## 9 STUDY AND DATA MANAGEMENT BY ASTRAZENECA

### 9.1 Training of study site staff

Before the first subject is entered into the study, an AstraZeneca representative/delegate will review and discuss the requirements of the Clinical Study Protocol and related documents with the investigational staff and also train them in any study specific procedures and *electronic data capture* system(s) utilised.

The Principal Investigator will ensure that appropriate training relevant to the study is given to all of these staff, and that any new information relevant to the performance of this study is forwarded to the staff involved.

The Principal Investigator will maintain a record of all individuals involved in the study (medical, nursing and other staff).

## **9.2 Monitoring of the study**

During the study, an AstraZeneca representative/delegate will have regular contacts with the study site, including visits to:

- Provide information and support to the Investigator(s)
- Confirm that facilities remain acceptable
- Confirm that the investigational team is adhering to the Clinical Study Protocol, that data are being accurately and timely recorded in the eCRF, that biological samples are handled in accordance with the Laboratory Manual and that study drug accountability checks are being performed
- Perform source data verification (a comparison of the data in the eCRF with the subject's medical records at the hospital or practice, and other records relevant to the study) including verification of informed consent of participating subjects. This will require direct access to all original records for each subject (e.g., clinic charts)
- Ensure withdrawal of informed consent to the use of the subject's biological samples is reported and biological samples are identified and disposed of/destroyed accordingly, and the action is documented, and reported to the subject.

The AstraZeneca representative will be available between visits if the Investigator(s) or other staff at the centre needs information and advice about the study conduct.

### **9.2.1 Source data**

Refer to the Clinical Study Agreement for location of source data.

### **9.2.2 Study agreements**

The Principal Investigator at each/the centre should comply with all the terms, conditions, and obligations of the Clinical Study Agreement, or equivalent, for this study. In the event of any inconsistency between this Clinical Study Protocol and the Clinical Study Agreement, the terms of Clinical Study Protocol shall prevail with respect to the conduct of the study and the treatment of subjects and in all other respects, not relating to study conduct or treatment of subjects, the terms of the Clinical Study Agreement shall prevail.

### **9.2.3 Archiving of study documents**

The Investigator follows the principles outlined in the Clinical Study Agreement (CSA).

### **9.3 Study timetable and end of study**

The end of the study is defined as ‘the last visit of the last subject undergoing the study’.

The study may be terminated at individual centres if the study procedures are not being performed according to GCP, or if recruitment is slow. AstraZeneca may also terminate the entire study prematurely if concerns for safety arise within this study or in any other study with Dapagliflozin / saxagliptin fixed dose combination.

### **9.4 Data management by delegate**

Data management will be performed by external partner, according to the Data Management Plan.

The data collected through third party sources will be obtained and reconciled against study data.

Adverse events and medical/surgical history will be classified according to the terminology of the latest version the Medical Dictionary for Regulatory Activities (MedDRA). Medications will be classified according to the WHO Drug Dictionary.

Data queries will be raised for inconsistent, impossible or missing data. All entries to the study database will be available in an audit trail.

The data will be validated as defined in the Data Management Plan. Quality control procedures will be applied to each stage of data handling to ensure that all data are reliable and have been processed correctly. The Data Management Plan will also clarify the roles and responsibilities of the various functions and personnel involved in the data management process.

When all data have been coded, validated, and locked, clean file will be declared. Any treatment revealing data may thereafter be added and the final database will be locked.

### **Serious Adverse Event (SAE) Reconciliation**

SAE reconciliation reports are produced and reconciled with the Patient Safety database and/or the investigational site.

## **10 ETHICAL AND REGULATORY REQUIREMENTS**

### **10.1 Ethical conduct of the study**

The study will be performed in accordance with ethical principles that have their origin in the Declaration of Helsinki and are consistent with ICH/Good Clinical Practice, applicable

regulatory requirements and the AstraZeneca policy on Bioethics and Human Biological Samples.

## **10.2 Subject data protection**

The Informed Consent Form will incorporate (or, in some cases, be accompanied by a separate document incorporating) wording that complies with relevant data protection and privacy legislation.

## **10.3 Ethics and regulatory review**

An Ethics Committee must approve the final Clinical Study Protocol, including the final version of the Informed Consent Form and any other written information and/or materials to be provided to the subjects. The Investigator will ensure the distribution of these documents to the applicable Ethics Committee, and to the study site staff.

The opinion of the Ethics Committee should be given in writing. The Investigator should submit the written approval to AstraZeneca before enrolment of any subject into the study.

The Ethics Committee should approve all advertising used to recruit subjects for the study.

AstraZeneca should approve any modifications to the Informed Consent Form that are needed to meet local requirements.

Before enrolment of any subject into the study, the final Clinical Study Protocol, including the final version of the Informed Consent Form, is approved by the national regulatory authority.

AstraZeneca will handle the distribution of any of these documents to the national regulatory authorities.

AstraZeneca will provide Regulatory Authorities, Ethics Committees and Principal Investigators with safety updates/reports according to local requirements.

## **10.4 Informed consent**

The Principal Investigator(s) at each centre will:

- Ensure each subject is given full and adequate oral and written information about the nature, purpose, possible risk and benefit of the study
- Ensure each subject is notified that they are free to discontinue from the study at any time
- Ensure that each subject is given the opportunity to ask questions and allowed time to consider the information provided

- Ensure each subject provides signed and dated informed consent before conducting any procedure specifically for the study
- Ensure the original, signed Informed Consent Form(s) is/are stored in the Investigator's Study File
- Ensure a copy of the signed Informed Consent Form is given to the subject
- Ensure that any incentives for subjects who participate in the study as well as any provisions for subjects harmed as a consequence of study participation are described in the informed consent form that is approved by an Ethics Committee.

### **10.5 Changes to the Clinical Study Protocol and Informed Consent Form**

If there are any substantial changes to the Clinical Study Protocol, then these changes will be documented in a new version of the study protocol.

The new version of the Clinical Study Protocol is to be approved by the relevant Ethics Committee and also the national regulatory authority approval, before implementation. Local requirements are to be followed for new versions of Clinical Study Protocols.

AstraZeneca will distribute any new versions of the Clinical Study Protocol to each Principal Investigator(s). For distribution to Ethics Committee see Section 10.3.

If a change to a Clinical Study Protocol requires a change to a centre's Informed Consent Form, AstraZeneca and the centre's Ethics Committee are to approve the revised Informed Consent Form before the revised form is used.

### **10.6 Audits and inspections**

Authorised representatives of AstraZeneca or delegate, a regulatory authority, or an Ethics Committee may perform audits or inspections at the centre, including source data verification. The purpose of an audit or inspection is to systematically and independently examine all study-related activities and documents, to determine whether these activities were conducted, and data were recorded, analysed, and accurately reported according to the Clinical Study Protocol, Good Clinical Practice (GCP), guidelines of the International Conference on Harmonisation (ICH), and any applicable regulatory requirements. The Investigator will contact AstraZeneca immediately if contacted by a regulatory agency about an inspection at the centre.

## **Appendix A Additional Safety Information**

### **Further Guidance on the Definition of a Serious Adverse Event (SAE)**

#### **Life threatening**

‘Life-threatening’ means that the subject was at immediate risk of death from the AE as it occurred or it is suspected that use or continued use of the product would result in the subject’s death. ‘Life-threatening’ does not mean that had an AE occurred in a more severe form it might have caused death (e.g., hepatitis that resolved without hepatic failure).

#### **Hospitalisation**

Outsubject treatment in an emergency room is not in itself a serious AE, although the reasons for it may be (e.g., bronchospasm, laryngeal oedema). Hospital admissions and/or surgical operations planned before or during a study are not considered AEs if the illness or disease existed before the subject was enrolled in the study, provided that it did not deteriorate in an unexpected way during the study.

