## 2 STUDY OBJECTIVES

### 2.1 Primary objective

Primary Objective:	Outcome Measure:
To describe the adverse events profile of dapagliflozin + saxagliptin fixed dose combinations in Indian T2DM patients at 24 weeks.	
 
• Adverse Events (AEs) including Serious adverse events (SAEs), AEs leading to discontinuation (DAE) and adverse events of special interest (volume depletion, renal events, major hypoglycaemic events, fractures, urinary/genital tract infections diabetic ketoacidosis, amputations and hospitalization for heart failure)
 
• Safety laboratory values
 
• Electrocardiogram (ECG)
 
• Vital Signs (pulse and BP)
 
• Physical examination
 

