### **5.3.5 Renal Events**

Renal events are defined by doubling of serum creatinine, dialysis and renal transplantation

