### **6.1 Definition of adverse events**

An adverse event is the development of any untoward medical occurrence in a subject or clinical study subject administered a medicinal product and which does not necessarily have a causal relationship with this treatment. An AE can therefore be any unfavourable and unintended sign (e.g. an abnormal laboratory finding), symptom (for example nausea, chest pain), or disease temporally associated with the use of a medicinal product, whether or not considered related to the medicinal product.

The term AE is used to include both serious and non-serious AEs and can include a deterioration of a pre-existing medical occurrence. An AE may occur at any time, including run-in or washout periods, even if no study treatment has been administered.

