### **6.2 Definitions of serious adverse event**

A serious adverse event is an AE occurring during any study phase (i.e., run-in, treatment, washout, follow-up), that fulfils one or more of the following criteria:

- Results in death
- Is immediately life-threatening
- Requires in-subject hospitalisation or prolongation of existing hospitalisation
- Results in persistent or significant disability or incapacity.
- Is a congenital abnormality or birth defect

- Is an important medical event that may jeopardize the subject or may require medical intervention to prevent one of the outcomes listed above.

For further guidance on the definition of a SAE, see Appendix A to the Clinical Study Protocol.

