### 6.3.6 Adverse events based on examinations and tests

The results from the Clinical Study Protocol mandated laboratory tests and vital signs will be summarised in the CSR. Deterioration as compared to baseline in protocol-mandated laboratory values and vital signs should therefore only be reported as AEs if they fulfil any of the SAE criteria or are the reason for discontinuation of treatment with the investigational product.

If deterioration in a laboratory value/vital sign is associated with clinical signs and symptoms, the sign or symptom will be reported as an AE and the associated laboratory result/vital sign will be considered as additional information. Wherever possible the reporting Investigator uses the clinical, rather than the laboratory term (e.g., anaemia versus low haemoglobin value). In the absence of clinical signs or symptoms, clinically relevant deteriorations in non-mandated parameters should be reported as AE(s).

Any new or aggravated clinically relevant abnormal medical finding at a physical examination as compared with the baseline assessment will be reported as an AE

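### Appendix A's planned-operation rule can leave an on-treatment amputation for pre-existing limb disease unrecorded if the disease is judged not to have worsened unexpectedly, although amputations are named in the primary outcome

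*Protocol*

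**What the plan says.** Section 2.1 and the synopsis list the special-interest AEs within the primary outcome, ending with "diabetic ketoacidosis, amputations and hospitalization for heart failure".

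Appendix A, under Hospitalisation, limits what counts as an AE: "Hospital admissions and/or surgical operations planned before or during a study are not considered AEs if the illness or disease existed". The illness must pre-date enrolment, and the sentence then adds a condition: "provided that it did not deteriorate in an unexpected way during the study". The protocol does not say what makes a deterioration unexpected, or who decides.

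Four other places bear on the point:

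- Section 6.1 says that an AE "can include a deterioration of a pre-existing medical occurrence".
- Section 6.2 defines a serious AE as an AE meeting at least one listed criterion, among them "Requires in-subject hospitalisation or prolongation of existing hospitalisation".
- Section 6.3.6 makes the following reportable as an AE when compared with baseline: "Any new or aggravated clinically relevant abnormal medical finding at a physical examination". Section 5.2.1 says much the same, and section 5.2.2 includes the extremities in the examination.
- Sections 5.3.1 to 5.3.6 give handling or definitions for hypoglycaemia, urinary and genital infections, volume depletion, ketoacidosis, renal events and heart-failure hospitalisation. For example: "Renal events are defined by doubling of serum creatinine, dialysis and renal transplantation". There is no corresponding section for amputations.

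**The concern.** An amputation is a surgical operation, so the Appendix A rule applies to it directly. If the rule covered only operations already scheduled at entry, it would remove events that could not be due to the study drug. It also covers operations planned during the study, when the subject is exposed. The protocol does not say that special-interest events are recorded regardless of this rule.

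This is a single-arm, descriptive safety study. The counts are the result, and no control arm is collected under the same rule. A recording rule that can remove an event from a named component of the primary outcome therefore acts in one direction only: the reported amputation count can be too low because of it, never too high. Because this is a rule about collection, a statistical analysis plan cannot repair it afterwards.

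**Working it through.** The protocol states no figure on this point. The check is mainly a reading of the text, with some arithmetic for scale.

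**Step 1. Can the rule apply to an enrolled subject?** It needs disease that existed before enrolment. The exclusion criteria in section 3.2 do not name peripheral arterial disease, foot ulcer or previous amputation. Criterion 10 lists cardiac and cerebrovascular events in the previous 3 months. Criterion 14 (systemic infections) and criterion 17 (investigator's judgement) may remove some such patients but not the category. By contrast, criterion 11 excludes a history of heart failure, which largely keeps the rule away from heart-failure admissions.

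**Step 2. Follow one case.** Limb disease is present at entry, an amputation is decided on and performed during treatment, and the course is judged expected.

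- Appendix A: the operation is not an AE.
- Section 6.2: a serious AE must first be an AE, so the operation is not a serious AE either, and the 24-hour reporting in section 6.4 is not triggered by it.
- Sections 5.2.1, 5.2.2 and 6.3.6: the worsened limb may be recorded as an AE through the physical examination, which Table 1 schedules at Visits 1, 2, 5, 7, 9 and 10. The recorded term may be the lesion and not the amputation.
- Sections 5.3.1 to 5.3.6: no provision for amputations.

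If the worsening is judged unexpected, the rule falls away and the operation stays an AE. The result turns on a word that the protocol does not define.

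**Step 3. Scale.** Inputs: N = 200 and 24 weeks of treatment (sections 4 and 8). Full exposure of all subjects is assumed.

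- Person-years: 200 × 24/52 = 92.3.
- Exact (Clopper-Pearson) 95% limits for x events in 200: lower = Beta quantile 0.025 with parameters (x, 200 − x + 1); upper = Beta quantile 0.975 with parameters (x + 1, 200 − x). For x = 0 the lower limit is 0 and the upper is 1 − 0.025^(1/200) = 1.83%.

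| Amputations counted | Incidence | Exact 95% CI | Per 100 person-years |
|---|---|---|---|
| 0 | 0.0% | 0 to 1.83% | 0 |
| 1 | 0.5% | 0.01% to 2.75% | 1.08 |
| 2 | 1.0% | 0.12% to 3.57% | 2.17 |

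**Step 4. How likely is any amputation at all?** The protocol gives no rate, so a range of 24-week risks is assumed. The chance of at least one event is 1 − (1 − p)^200:

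| Assumed risk p | Chance of at least one in 200 |
|---|---|
| 0.1% | 18% |
| 0.25% | 39% |
| 0.5% | 63% |
| 1.0% | 87% |

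These are chances of any amputation. Nothing in the protocol allows an estimate of the share that Appendix A would remove.

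**The case against.** The strongest reply is that the gap is narrow and partly guarded. The condition in Appendix A keeps an amputation as an AE when the disease worsens unexpectedly, and in a patient judged fit for a 24-week study, a limb that later needs amputation would often be judged unexpected. Criterion 17 lets the investigator exclude patients at evident risk. A worsened foot lesion or a newly missing digit is an examination finding that sections 5.2.1 and 6.3.6 require to be reported. All of this stands, and it limits the number of cases. It does not close the gap: the condition depends on an undefined judgement, and the examination rules secure the finding without securing the amputation as a counted event.

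Three stronger readings are tempting, and the document does not support them:

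- *That Appendix A removes planned amputations outright, so that they are never counted.* The condition on unexpected deterioration and the examination rules rule this out.
- *That Appendix A contradicts section 6.1.* Section 6.1 is about the deterioration of a condition, and Appendix A is about the admission or operation. Both can hold together: the worsening is reportable and the procedure is not an AE in itself.
- *That no form would capture an amputation.* The protocol states none, but the eCRF and its completion guideline are not shown. Detailed special-interest definitions may also properly sit in the analysis plan.

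It is also fair to say that the confidence limits above would apply to any rare event. They show what one lost event does to the reported result, not how many would be lost.

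**Conclusion.** The point holds in limited form. Following Appendix A as written, an amputation performed on study drug for limb disease present at enrolment, and judged to have progressed as expected, can go unrecorded as an AE or serious AE. Amputations are nevertheless a named part of the primary outcome.

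The number of such cases is unknown and probably small. If one is missed, the report shows 0/200 with an upper limit of 1.8% instead of 1/200, or 0.5%, with limits 0.01% to 2.8%. On an annualised basis it shows zero instead of about 1.1 per 100 person-years. The figures assume 200 treated subjects with full 24-week exposure. That even one such event would occur is an assumption, not something the protocol states.

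**What to change.** Add one sentence to Appendix A, under Hospitalisation, and repeat it in the eCRF completion guideline. Suggested wording: *This exclusion does not apply to amputations. Every amputation performed after the first dose and within the adverse event collection period is recorded as an adverse event of special interest, whether or not the underlying disease existed at enrolment and whether or not the operation was planned.*

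Add a flag for operations already scheduled before the first dose, so that the summary can show them separately.

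The cost is one sentence and one data field. No visit, test or procedure is added, and clinical management is unchanged. The downside is that the amputation count may rise slightly with events unrelated to the product. The flag identifies those already scheduled before dosing, and the investigator's causality rating in section 6.3.4 covers the rest.

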#### **Important medical event or medical intervention**

Medical and scientific judgement should be exercised in deciding whether a case is serious in situations where important medical events may not be immediately life threatening or result in death, hospitalisation, disability or incapacity but may jeopardize the subject or may require medical intervention to prevent one or more outcomes listed in the definition of serious. These should usually be considered as serious.

Simply stopping the suspect drug does not mean that it is an important medical event; medical judgement must be used.

- Angioedema not severe enough to require intubation but requiring iv hydrocortisone treatment
- Hepatotoxicity caused by paracetamol (acetaminophen) overdose requiring treatment with N-acetylcysteine
- Intensive treatment in an emergency room or at home for allergic bronchospasm
- Blood dyscrasias (e.g., neutropenia or anaemia requiring blood transfusion, etc.) or convulsions that do not result in hospitalisation

Development of drug dependency or drug abuse

#### **A Guide to Interpreting the Causality Question**

When making an assessment of causality consider the following factors when deciding if there is a ‘reasonable possibility’ that an AE may have been caused by the drug.

- Time Course. Exposure to suspect drug. Has the subject actually received the suspect drug? Did the AE occur in a reasonable temporal relationship to the administration of the suspect drug?
- Consistency with known drug profile. Was the AE consistent with the previous knowledge of the suspect drug (pharmacology and toxicology) or drugs of the same pharmacological class? Or could the AE be anticipated from its pharmacological properties?
- De-challenge experience. Did the AE resolve or improve on stopping or reducing the dose of the suspect drug?
- No alternative cause. The AE cannot be reasonably explained by another aetiology such as the underlying disease, other drugs, other host or environmental factors.
- Re-challenge experience. Did the AE reoccur if the suspected drug was reintroduced after having been stopped? AstraZeneca would not normally recommend or support a re-challenge.
- Laboratory tests. A specific laboratory investigation (if performed) has confirmed the relationship.

In difficult cases, other factors could be considered such as:

- Is this a recognized feature of overdose of the drug?
- Is there a known mechanism?

Causality of 'related' is made if following a review of the relevant data, there is evidence for a 'reasonable possibility' of a causal relationship for the individual case. The expression 'reasonable possibility' of a causal relationship is meant to convey, in general, that there are facts (evidence) or arguments to suggest a causal relationship.

The causality assessment is performed based on the available data including enough information to make an informed judgment. With limited or insufficient information in the case, it is likely that the event(s) will be assessed as 'not related'.

Causal relationship in cases where the disease under study has deteriorated due to lack of effect should be classified as no reasonable possibility

